Patient Selection: 276 parents of Medicaid-insured children ages 2-12 years inclusive, seeking asthma care at Seattle Children’s or Mary Bridge Children’s emergency department who are the primary owners of a mobile phone with text messaging service.

Outcomes: Outcome data on parental self-efficacy and outcome expectations, adherence to asthma care treatment recommendations (e.g. primary care utilization), and child

asthma outcomes (e.g., ED visits, asthma morbidity) will be collected via structured telephone interviews at 3, 6, 12, 18, and 24 months post- enrollment.

Study Aims & Hypotheses

Aim 1: To improve urban, low-income children’s asthma-related health outcomes (primary outcome: reduced ED visits for asthma care, secondary outcome: lower morbidity) over 12 months.

Hypothesis 1a: Children of parents who receive T2B will make fewer ED visits for asthma care than those receiving standard ED asthma care alone.

Hypothesis 1b: Parents who receive T2B will report lower morbidity (i.e., days of impairment) than those receiving standard care.

Aim 2: To improve adherence to asthma care guidelines (primary care utilization for asthma care and improved parent asthma care self-management) over 12 months.

Hypothesis 2a: Parents who receive T2B will report increased primary care utilization (i.e., more frequent follow-up with their child’s PCP for routine asthma care) than those receiving standard care.

Hypothesis 2b: Parents who receive T2B will demonstrate greater knowledge of asthma self-management than those receiving standard care.

Hypothesis 2c: Primary care utilization and improved self-management will mediate the effect of T2B on children’s asthma-related health outcomes.

Aim 3: To improve parent cognitions (parental self-efficacy and outcome expectations) regarding partnering with their child’s PCP for asthma care over 12 months.

Hypothesis 3a: Parents who receive T2B will report greater self-efficacy in communicating with their child’s PCP about their child’s asthma care and greater outcome expectations for effective treatment and control of their child’s asthma symptoms than those receiving standard care.

Hypothesis 3b: Parental self-efficacy and outcome expectations will mediate the effect of T2B on adherence to asthma care guidelines.

Background and Study Rationale

Pediatric Asthma Epidemiology

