Asthma Self-Management: For asthma, self-management involves a number of tasks to prevent and manage symptoms, such as monitoring symptoms over time, avoiding known triggers, and taking medications properly. The Asthma Self-Management Questionnaire,⁷⁹ a newly developed measure recommended by experts convened for the Asthma Outcomes workshop,⁸⁰ includes 16 multiple-choice questions regarding knowledge of preventive strategies and controller medication use. Standardized scores (0-100) are generated, with higher scores indicating more knowledge of self-management. Cronbach’s alpha was 0.71. Wording of questions will be revised (e.g., “you” = “your child”) to be appropriate for parents of children with asthma.

Parental Self-efficacy: The Medical Competence Communication Scale (MCCS) measures patient’s perceptions of their own communication during their most recent medical visits.⁸¹ The patient version of the measure is used to assess information giving, seeking and verifying, as well as socio-emotional communication. The MCCS, patient version, consists of 23 items rated on a 5-point Likert scale (1= unimportant to 5= important) with a higher score indicating greater perception of communication competence. Cronbach’s alpha ranges from 0.76-0.92 on the various subscales. Only the 16 self-competence items will be administered in this study. Wording of questions will be modified to state “my child’s medical problem” rather than “my medical problem.” The Parent Asthma Management Self-Efficacy Scale (PAMSES) is a valid and reliable instrument designed to measure parent self-efficacy in preventing and managing children’s asthma attacks.⁸² The PAMSES consists of 13 items rated on a 5-point Likert scale (1=not at all sure to 5=completely sure) with a total possible score range of 13 to 65; higher scores indicate greater self-efficacy. Cronbach’s alpha in a sample of primarily White mothers was 0.87.⁸²

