In **Aim 3**, we will use linear regression models, as above, to evaluate the intervention effect on measures of self-efficacy and outcome expectations. We will then use path analysis to assess whether parental self-efficacy and outcome expectations (defined using the three validated instruments) mediate intervention effects on PCP follow-up rates and knowledge of self-management. Although the data collected at the 12-month time point will be used as our primary indicator of intervention effectiveness, we will also utilize data collected through the full 24-month follow-up period to evaluate sustainability of the hypothesized effects of the intervention in the same series of analyses. The above analyses estimate the impact of the intervention at observed levels of acceptance of the intervention and thus estimate the expected average effectiveness of the intervention if implemented in a similar population. We will also estimate the magnitude of the effect on each outcome under alternative levels of engagement in the intervention to provide a range of estimated effects based on greater and lesser levels of engagement. Moreover, we will examine potential moderating effects of race/ethnicity on the intervention effects.

C.5.c: Sample Size Estimate

All sample size and power analyses are based on a 2-tailed type 1 error of 5% in final analyses based on 12 month follow-up results. For the primary outcome under **Aim 1** (number of ED visits for asthma care during a 12-month interval), we calculated that a sample size of 125 per study group provides at least 90% power to detect a clinically important 35% reduction in the T2B group compared to the estimated average rate of 1.28 ED visits per year in the usual care group (based on 2012 ED records). For the primary outcome under **Aim 2** (number of PCP visits for asthma care during a 12-month interval), we calculated that a sample size of 120 participants per group provides 90% power to detect an increase to the recommended 3 annual visits in the T2B group over the observed rate of 1.8/year in the previous IMPACT DC sample.⁷ For the other outcomes under Aim 3 (self-efficacy and outcome expectation), a sample size of 85 per group provides 90% power to detect a 0.5 SD effect size difference between study groups. A feasible **analytic sample size of 110** ensures >80% power in all aforementioned analyses.

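### The protocol gives the MCCS importance response anchors but scores it as communication competence; fielded as written, Hypothesis 3a's only communication measure would record something else

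*Protocol*

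**What the plan says.** **Protocol, Data Collection, Parental Self-efficacy.** The MCCS "measures patient’s perceptions of their own communication during their most recent medical visits". The patient version is described as having 23 items, "rated on a 5-point Likert scale (1= unimportant to 5= important) with a higher score indicating greater perception of communication competence". Two adaptations are stated. One is the subset used: "Only the 16 self-competence items will be administered in this study". The other is that items refer to the child's medical problem instead of the respondent's own. No change of response options is mentioned.

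**Same paragraph, second scale.** The Parent Asthma Management Self-Efficacy Scale (PAMSES) is "designed to measure parent self-efficacy in preventing and managing children’s asthma attacks". Its anchors run from not at all sure to completely sure.

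**Protocol, Parental Outcome Expectations.** An 8-item scale on expectations for asthma treatment, answered from strongly disagree to strongly agree.

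**Protocol, Study Aims & Hypotheses.** Hypothesis 3a is that T2B parents will "report greater self-efficacy in communicating with their child"'s PCP, together with greater outcome expectations. Hypothesis 3b makes self-efficacy and outcome expectations mediators of adherence.

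**SAP C.5.b, Aim 3.** Linear regressions are planned for the measures of self-efficacy and outcome expectations. Path analysis then takes as mediators "parental self-efficacy and outcome expectations (defined using the three validated instruments"). The SAP does not say which instrument tests which part of Hypothesis 3a.

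**The concern.** Valuing communication and being able to do it are different things. A parent may hold that asking the doctor questions matters a great deal and still feel unable to ask them. The protocol's own theory separates the two. Its Conceptual Framework section defines self-efficacy as the belief that one can carry out a task. Its Lessons Learned section treats beliefs about the costs and benefits of a behaviour as a separate cognition, outcome expectations. An importance rating lies closer to the second than to the first.

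Communication self-efficacy is the mechanism the intervention was built to change. If its only measure records importance, two errors are possible:

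- **False null.** Parents gain confidence or skill, but their view of how much communication matters does not move.
- **False positive.** The programme stresses that communication matters. The PEPAC section emphasises the importance of planning for the visit, and a sample text message in Table 1 tells parents that saying the plan back is important. Intervention parents could repeat that message on an importance scale with no gain in ability.

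**Working it through.** The main check is textual. A power calculation follows to show what is and is not affected.

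**1. Do anchors and construct agree for each Aim 3 instrument?**

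| Instrument | Construct stated in the protocol | Anchors stated (1 to 5) | Agree? |
|---|---|---|---|
| MCCS, 16 self-competence items | Own communication at recent medical visits | unimportant to important | No |
| PAMSES, 13 items | Self-efficacy in preventing and managing attacks | not at all sure to completely sure | Yes |
| Outcome expectations, 8 items | Expectations for asthma treatment | strongly disagree to strongly agree | Yes |

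Only the MCCS row conflicts, and it does so within one sentence. Neither document corrects or explains it.

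**2. Does another instrument cover communication with the PCP?** No. The PAMSES concerns attacks and the expectations scale concerns treatment. The MCCS alone addresses the communication part of Hypothesis 3a, and it is one of the three instruments behind the Hypothesis 3b mediators.

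**3. Would planned checks catch it?** Not reliably. SAP C.5.a plans Cronbach's alpha for all standardised instruments. Alpha measures internal consistency, and importance ratings can be highly consistent while measuring the wrong thing. The Data Collection section has every measure except the Asthma Self-Management Questionnaire given at each wave, so the error would repeat throughout follow-up.

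**4. Is the Aim 3 sample size affected?** Inputs from SAP C.5.c: two-sided 5%, 90% power, effect 0.5 SD.

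- n per group = 2(1.960 + 1.282)² / 0.5² = 2 × 10.51 / 0.25 = 84.1, so 85. This is the SAP's figure. The t-test calculation gives 85.03, with 90.0% power at 85.
- Analytic sample of 110, read as per group because 110 / 0.80 = 137.5, so 138 enrolled per group, as stated. Power = Φ(0.5 × √(110/2) − 1.960) = Φ(1.748) = 96.0%.

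These figures are in SD units, so correcting the anchors changes none of them.

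**5. Illustration of the false-null direction, by assumption.** Suppose T2B moves competence by 0.5 SD and moves the importance rating only through its correlation r with competence, so that the observed effect is 0.5r. The documents give no r. Power at 110 per group is Φ(0.5r × 7.416 − 1.960):

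| r | Effect (SD) | Power |
|---|---|---|
| 1.0 | 0.5 | 96% |
| 0.8 | 0.4 | 84% |
| 0.6 | 0.3 | 60% |
| 0.4 | 0.2 | 32% |
| 0.2 | 0.1 | 11% |

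This does not cover the false-positive direction, where T2B acts on the importance rating directly. Nothing in the documents allows that to be sized.

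**The case against.** The best reply is that the anchors stand in a sentence about the published 23-item instrument, whereas the trial fields 16 items on a form that the protocol cites as an appendix, the Baseline Survey. Everything else in the paragraph points to competence: own communication at recent visits, self-competence items, a competence score. A slip in describing a sound questionnaire fits this text at least as well as a faulty questionnaire does. That stands. It makes the consequence conditional, but it does not remove the contradiction.

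Four stronger readings are tempting, and the documents do not support them:

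- **Scores will sit near the ceiling at baseline.** No item wording, mean or SD for the MCCS is given, so no ceiling can be asserted or sized. The baseline means, medians and ranges planned in SAP C.5.a would show one if it arose.
- **The SAP pools the PAMSES with the MCCS.** It refers to models and measures in the plural, and the mention of three instruments lists them without defining a composite. What is missing is a statement of which instrument tests which claim.
- **Importance-anchored baselines cannot be used as a covariate.** In a randomised comparison, a pre-randomisation covariate need not share the outcome's scale. A weaker correlate costs precision, not validity.
- **The trial's main result is at risk.** The point concerns one of three Aim 3 instruments. It does not touch ED visits, the rest of Aim 1, or any sample-size figure.

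**Conclusion.** Wrong as written. The protocol states importance anchors for a scale that it scores and interprets as competence, and neither document resolves the conflict. If the anchors are fielded as stated, the communication part of Hypothesis 3a has no valid measure, one contributor to the Hypothesis 3b mediators is mislabelled, and the direction of error is not known in advance.

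A reader might infer that the questionnaire itself is faulty. The documents do not show that, because the survey appendix is not in the text available here. The size of the effect on Aim 3 is also unknown: the power range of 96% down to 11% rests wholly on an assumed correlation between 1.0 and 0.2. The finding warrants a correction in the plan. It does not call the primary analysis or the sample size into question.

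**What to change.** 1. **Check the Parental Self-efficacy paragraph against the fielded survey.**
   - If only the description is wrong, correct the anchors there. The cost is one line of protocol text.
   - If the survey uses importance anchors, replace them at all waves with anchors that suit self-rated performance at recent visits. The agreement scale already used for outcome expectations would serve. The PAMSES sureness scale fits less well, because it rates confidence while these items ask about past visits. The cost is a change of response labels, with no extra interview time.
2. **Do not report scores already collected on importance anchors** as communication competence or self-efficacy for Hypotheses 3a and 3b. Record which form each participant answered at each wave. Such a score taken before randomisation may still be used as a covariate, with some loss of precision.
3. **Add a sentence to SAP C.5.b, Aim 3,** naming the MCCS self-competence score as the measure for the communication part of Hypothesis 3a, with the PAMSES reported separately as asthma-management self-efficacy.

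No change to the sample size is needed.

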**Text2Breathe: Enhance Parent Communication
to Reduce Pediatric Asthma Disparities**

Study Protocol

Principal Investigator: [name], MBA

Version 6

March 15, 2017

Objective/Aims: With the goal of reducing disparities in pediatric asthma morbidity and urgent care reliance, we will test the efficacy of a mHealth HC intervention (“Text2Breathe” – T2B) designed to equip urban, low-income parents with tools for more effectively communicating with their children’s PCPs and managing their child’s asthma. Aim 1: To improve urban, low-income children’s asthma-related health outcomes (primary outcome: reduced ED visits for asthma care, secondary outcome: lower morbidity) over 12 months. Aim 2: To improve adherence to asthma care guidelines (primary care utilization for asthma care and improved parent asthma care self-management) over 12 months. Aim 3: To improve parent cognitions (parental self-efficacy and outcome expectations) regarding partnering with their child’s PCP for asthma care over 12 months.

Rationale: Chronic diseases, such as asthma, disproportionately affect urban, low-income children. A key recommendation of the National Asthma Education and Prevention Program (NAEPP) Guidelines for the Diagnosis and Management of Asthma is partnership between healthcare providers and patients (and their parents, for children). Facilitating parents’ open communication with providers regarding healthcare status and concerns can equip them to more effectively partner with their child’s primary care provider (PCP). Thus, improving the health communication skills of low-income parents could improve parent’s adherence to treatment recommendations including utilization of the primary care for asthma care, and ultimately improve their child’s asthma health outcomes. Delivering content via mobile technology, part of a growing field called “mobile health” or “mHealth”, may be particularly useful among lower-income, urban families for whom the use of mobile and text messaging is widespread as an available and efficient means of communication.¹⁰

Study Design: A parallel-groups randomized control trial with low-income parents of children with physician-diagnosed asthma, ages 2-12 years inclusive, who are seen in the Seattle Children’s ED or Mary Bridge Children’s [for asthma care]. Each hypothesis will be tested by contrasting parents receiving T2B with parents receiving only standard ED-based care for their child’s asthma, over 12 months.

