enhanced HC intervention to parents of children with other chronic conditions. In addition, the expedience of scaling up a text-message protocol means that our intervention can easily be adapted to reach a broader audience in a cost-effective manner when compared to ongoing face-to-face interventions. If efficacy is demonstrated, another next step will be to expand the program to other healthcare settings, such as primary care practices.

Study Design

We propose to conduct a RCT with low-income parents of children with physician-diagnosed asthma, ages 2-12 years inclusive, who are seen in the Seattle Children's or Mary Bridge Children's ED [for asthma care] to test the efficacy of our mHealth HC intervention, T2B, primarily for reducing ED/urgent care visits for asthma care. Each hypothesis will be tested by contrasting parents receiving T2B with parents receiving only standard ED-based care for their child's asthma, over 12 months.

Study Schedule

Data on child and parent outcomes will be collected in-person at enrollment and by telephone interviews at 3, 6, and 12 months post-enrollment. These telephone interviews will all be coordinated and conducted by the Seattle Children's study staff. Given the highly seasonal nature of asthma-related morbidity, the text message component of the intervention will continue for 12 months (3 months of biweekly educational interactive text messages; ongoing parent-initiated access to key messages and reminder text messages for PCP follow-up/medication refills/annual flu vaccines) allowing for the capture of individual variability in disease course. (Figure 3).

[figure not shown]

Figure 3

Study Population

The study population will be parents/guardians of Medicaid- insured patients seen in the Seattle Children’s or Mary Bridge Children’s ED for treatment of their asthma. These are patients whose asthma is not yet well controlled and who experience the greatest morbidity due to environmental and social factors and are thus the most resource-intensive group.

Inclusion criteria: Parents of Medicaid-insured children age 2 to 12 years inclusive with physician- diagnosed asthma for at least 12 months will be eligible. Older children/adolescents are excluded because they assume greater responsibility for asthma self-management, and their communication with providers becomes more independent over time. Parents must be

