the primary owners of a mobile phone with text messaging service, which is anticipated to be at least 75% of parents in this population based on previous research on urban, low-income parents.^{59, 60}

Exclusion criteria: Parents of children with significant medical co-morbidities (e.g., sickle cell disease, insulin-dependent diabetes mellitus) will be excluded because of their increased interaction with healthcare providers.

Recruitment and Randomization

CRA's will identify potentially eligible patients through electronic admission board and medical record diagnostic codes after intake into the ED, and they will describe the study to potentially eligible parents while they are waiting to be seen by a provider. Interested families will be screened for eligibility. If eligible, parents will complete the consent process. (See section 5.2.a for more details.) Then the CRA will administer a baseline questionnaire focusing on health care utilization, asthma self-management and morbidity, parental self-efficacy and outcome expectations. After the questionnaire is completed, participants will be randomized to usual care or the intervention group (T2B). Randomization will occur automatically via the RedCap database system. Time allowing, participants randomized to the intervention will receive brief education on the 3 S's and orientation to the text message component (including an "opt-in" code) while in the ED or if necessary by phone within 48 hours. The text message education component will begin within 1 week after participants are randomized, allowing time for participants to enter the opt-in code.

Retention and Compensation

Parents will receive total compensation of \$110 for participation in the study to be dispensed as: \$20 gift card will be given to the parent after he/she completes the baseline interview and \$30 gift cards will be sent after the 3, 6, 12 follow-up interviews; Based on previous studies conducted by our research team with similar populations, this amount should be sufficient to compensate participants for their time and offset the cost incurred for the text messages (if any), but it will not be coercive, minimizing participation solely based on financial gain.

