Parental Outcome Expectations: In accordance with other research of pediatric asthma interventions, to assess parents’ beliefs about possible asthma quality of life for their child we will administer an 8-item measure of parental expectations for asthma treatment.⁸³ Parents respond to statements about their expectations (e.g., “I believe that my child can be symptom free most of the time.”) using a 5-point Likert scale (1=strongly disagree to 5=strongly agree). Total scores are calculated by averaging across responses, and higher scores reflect more optimistic asthma outcome expectations (Cronbach’s alpha = 0.70).

Study Intervention

The T2B intervention will consist of a personalized, interactive text-messaging program with asthma and health communication education (derived from IMPACT DC and PEPAC), as well as follow-up reminders for scheduling asthma care appointments with PCP and annual flu vaccines. Participants randomized to the control group will also receive reminder texts to schedule with their child's PCP and to get an annual flu shot. An algorithm of text message delivery will be determined for each participant (see appendix for Sample Algorithm content). The manual/intervention protocol and text messaging content will be refined and finalized during the start-up phase of the project (see Protection of Human Subject section for timeline). Within 24 hours of enrolling in the study, participants in the intervention will begin receiving a series of automated bidirectional text messages to their mobile phones based on the education components of IMPACT DC and PEPAC. In order to be oriented and familiar with the content of these messages participants randomized to intervention will also receive face-to-face PEPAC education, including the 3S tool kit card during their baseline visit. Messages will originate from the T2B program during the first 3 months, after which parents can text key words to repeat or receive additional messages/education at any time.

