In **Aim 2**, we will implement a negative binomial regression model to estimate the IRR and 95% CI for number of follow-up visits with the PCP for asthma care over 12 months in the intervention group compared to the usual care group. In addition to the group variable, the model will include a covariate to account for PCP visit frequency prior to randomization. The exponentiated form of the coefficient of the group term will reflect the relative difference between groups in annual rate of PCP follow-up visits for asthma care. We will use linear regression models to examine the intervention effect on knowledge of self-management (continuous scale score). The model independent variables will include study group and pre-randomization level of knowledge of self-management. The magnitude of the group coefficient will provide an estimate of the size and direction of difference between groups controlling for differences in pre-randomization levels.

We will also assess whether primary care utilization (annual rate of follow-up visits) and increased knowledge of self-management mediate the relationship between the assigned communication intervention and child asthma outcomes (defined as frequency of ED and urgent care visits for asthma care and days of impairment). To do so, we will use path analysis models at baseline and each follow-up time separately. To test these hypotheses using longitudinal data, growth trajectories of each outcome will be modeled using multi-process latent growth models (LGM) of these

proximal and distal outcomes. The hypothesized mediating effects of the proximal outcomes will be tested by relating the intervention condition, the latent slope growth factors of the multiple growth processes, and the distal outcomes.⁸⁶

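### Controls also get PCP and flu reminder texts, so the trial tests T2B against standard ED care plus reminders, not against standard ED care alone

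*Protocol*

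**What the plan says.** The Protocol names the comparator several times. The opening summary and the main Study Design section share one sentence: "Each hypothesis will be tested by contrasting parents receiving T2B with parents receiving only standard ED-based care". Hypothesis 1a, on the primary outcome, predicts that children of T2B parents "will make fewer ED visits for asthma care than those receiving standard ED asthma care alone".

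The other between-group hypotheses (1b, 2a, 2b, 3a) use a looser term. Hypothesis 2a, for example, ends "PCP for routine asthma care) than those receiving standard care". The Recruitment and Randomization section calls the arm usual care. SAP C.5.b compares PCP visits "over 12 months in the intervention group compared to the usual care group", and C.5.c uses the same label when planning for ED visits.

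The Study Intervention section describes what is delivered. T2B is a text-messaging programme with education, "as well as follow-up reminders for scheduling asthma care appointments with PCP and annual flu vaccines". The next sentence reads: "Participants randomized to the control group will also receive reminder texts to schedule with their" child's PCP, and it adds the annual flu shot. The Study Schedule section and Table 1 also list PCP and flu reminders as T2B content.

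**The concern.** Controls who are sent study reminder texts are not receiving standard ED care only. A result reported against the hypotheses as worded would therefore be a conclusion about a comparator that the trial does not have.

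The two reminders are not incidental. They are part of the T2B package, and the PCP reminder prompts the Aim 2 outcome directly. PCP use is also one of the proposed mediators of T2B's effect on child outcomes (Hypothesis 2c). If PCP visits do not differ between arms, a reader of Hypothesis 2a would conclude that T2B adds nothing to standard care. The data would support only the statement that no gain was detected beyond the reminders.

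**Working it through.** No stated figure is in dispute, so the check sets the texts side by side and works out what the comparison estimates.

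**1. Comparator as named, against control care as delivered**

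| Place | Comparator wording | Fits the control reminders? |
|---|---|---|
| Protocol, summary design paragraph | *only* standard ED care | No |
| Protocol, Study Design | *only* standard ED care | No |
| Protocol, Hypothesis 1a | standard ED care *alone* | No |
| Protocol, Hypotheses 1b, 2a, 2b, 3a | standard care | Silent on the reminders |
| Protocol, Recruitment and Randomization | usual care | Silent |
| SAP C.5.b (Aim 2) and C.5.c (Aim 1) | usual care group | Silent |
| Protocol, Study Intervention | controls get PCP and flu reminder texts | This is what is delivered |

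**2. Could the reminders be part of standard ED care?** The documents do not define the content of standard ED care. Nothing in them describes the texts as part of it. The control reminders appear under Study Intervention, directly after the same two reminders are listed as T2B components. The SAP does not mention them for the control arm. The natural reading is that the study adds them.

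**3. What is estimated.** Let m(T) be the mean outcome rate under T2B, m(S+R) the rate under standard ED care plus the control reminders, and m(S) the rate under standard ED care alone. Then

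m(T)/m(S) = [m(T)/m(S+R)] × [m(S+R)/m(S)].

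The left side is the contrast that the design statement and Hypothesis 1a name. The first factor on the right is what the negative binomial models in SAP C.5.b estimate. The second factor is the effect of the reminders themselves. No arm receives S alone, and the documents give no figure for a reminder effect, so that factor can be neither estimated nor bounded.

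**4. Consequence by outcome**

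- PCP visits (2a): if the reminders work as intended, the second factor exceeds 1 and the estimated ratio is smaller than the ratio against standard ED care alone. If they have no effect, the two ratios are equal.
- ED visits (1a): on the plan's own mediation model (2c), any rise in control PCP visits could lower control ED visits. Whether it does, and by how much, is not given.
- A positive finding shows benefit beyond the reminders. A null shows no detected benefit beyond them and leaves T2B against standard ED care alone untested.

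**5. Sample size.** The enrolment target follows from SAP C.5.c: 110/0.80 = 137.5, so 138 per group and 276 in total. Correcting the comparator's name does not alter it.

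**The case against.** The strongest reply is that the Protocol discloses the control reminders openly in the section that governs delivery, and that giving them to both arms is a sensible design. On this view, standard care and usual care are ordinary shorthand that does not exclude a co-delivered reminder, and the SAP never says only or alone. Much of this stands. The looser labels are incomplete rather than contradictory, the reminders are worth keeping, and the correction is one of wording. The reply does not cover the two design statements and Hypothesis 1a, whose wording rules out any addition and which define what the trial claims to test.

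A reader might infer more than the documents support:

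- **That the comparison is biased.** It is not. Randomisation gives a valid comparison of the two arms as delivered; only the description of one arm is wrong.
- **That the Aim 2 power is wrong**, because the planning rate of 1.8 PCP visits a year makes no stated allowance for control reminders. The documents give neither a reminder effect nor the dispersion behind the calculation. The 1.8 comes from an earlier IMPACT DC sample and is not shown to be a rate under standard ED care. If both arms rose in proportion, the planned ratio of 3/1.8 = 1.67 would not change.
- **That the SAP's remark about average effectiveness in a similar population (C.5.b) commits it to the wrong comparator.** That remark concerns levels of uptake and engagement, not control care.
- **That the arms are known to differ in refill reminders or interactive prompts.** Refill reminders appear once, in Study Schedule, and not among the reminders in Table 1. The frequency and interactivity of the control texts are not stated. Neither difference is established.

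**Conclusion.** The point holds as a misstatement of the comparator. It is explicit in three places (the summary design paragraph, the Study Design section and Hypothesis 1a) and is an omission wherever standard care or usual care is used without definition. The trial estimates T2B against standard ED-based care plus PCP and flu reminder texts. The effect on interpretation is greatest for Hypothesis 2a and for the PCP-visit mediator in 2c, but it reaches the primary hypothesis as well.

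The numerical gap between the named and the estimated contrast is unknown. It could be nil if the reminders do nothing. The conclusion rests on two assumptions: that controls are sent the texts as the Study Intervention section says, and that such texts are not already part of standard ED care, which the documents never suggest. No sample size or power figure needs to change on this account. It should be corrected because the plan's stated conclusion would otherwise refer to a group that was not studied.

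**What to change.** Keep the control reminders, and then:

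1. In the summary design paragraph, the Study Design section and Hypothesis 1a, remove *only* and *alone*. Name the comparator as standard ED-based care plus text reminders to book with the PCP and to have the yearly flu vaccination.
2. Define standard care and usual care once in those terms. Apply the definition to the other hypotheses, the randomisation text and the SAP group label.
3. State in the SAP and in any report that the results, including a null on PCP visits, concern the effect of T2B beyond those reminders.
4. Do not list refill reminders or interactive prompts as part of that added effect unless the control text algorithm confirms that controls do not receive them.

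The cost is wording in two documents, with no extra participants, visits or data. The real price is a narrower claim: the trial can no longer say that it measured the whole T2B package against standard ED care alone.
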